The Berlin Consensus 2016 Concussion in Sport Group (CISG)¹, which recently updated The Zurich Consensus³¹, has provided guidelines for return to play for adult athletes which major sport and prevention institutions are readily adopting. These consensus statements were originally designed to provide general recommendations for the management of sport concussion in adults, with the pediatric population being considered in subsequent more recent versions.

While children and youth do present with similar post-concussion symptoms as adults, several investigators and The Berlin Consensus ¹ have noted the need for a more conservative approach for their concussion management due to the unique physiological

make-up among the pediatric patients. ³²⁻³⁴The CanChild Protocols for Concussion Management for children and youth 5-18 years ³⁵⁻³⁷ used in this proposed study were developed with reference to the consensus statements. ¹ The CanChild protocols highlight the need for graduated RTA and RTS management strategies that reflect the pattern of recovery that is unique to each child/youth. Focusing on an individual's unique pattern of recovery may better reflect the complicated course of healing that requires more than a 'one size fits all' set of recommendations.

There are five stages in the CanChild RTS protocol² and six stages in the RTA protocol.² In these protocols, all children/youth are advised that there can be no high-level physical activity or contact sport while symptoms are present. However, 'rest' does not equate to social isolation or sensory deprivation. Daily activities that can be tolerated for each stage of recovery, without symptom exacerbation, are identified in the Activity Suggestions supplement that accompany the protocols, both of which are available on the CanChild website.² Families often find it difficult to gauge the appropriate amount of activity, including cognitive effort, for their child/youth's stage of recovery. The therapeutic goal in managing concussion recovery is to find the individual's level of cognitive and physical exertion that promotes healing which is the focus of our proposed Back2Play App. This graded approach was highlighted in a recent systematic review comparing the difference in concussion management in children/youth versus adults that was part of the CISG 2016 meeting in Berlin.¹ Importantly, this systematic review identified the need for an effective pediatric specific concussion management protocol.³⁸

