Appendix 1.1 Business Rules for In-App Notifications

Progression through the CanChild RTA/RTS Guideline

- 1. Participants cannot enter RTA Stage 4 until they have completed RTS Stage 1-3
 - o If the participant reports RTA Stage 4 when they are in RTS Stage 1 or 2 they will receive the message "Stage 1, 2 and 3 come before RTA Stage 4!"
- 2. Participants must complete RTS Stage 5 (Full Return to School) before they can enter RTA Stage 4.
 - If the participant reports RTA Stage 4 or 5 when they are in RTS Stage 3 through 5, they will receive the message "You should complete RTS Stage 4-5 before RTA Stage 4-6".
- 3. Participants will be recommended to move to Stage 2 of RTS after 7 days
 - o If the participant reports RTS Stage 1 for 7 days, they will receive the message "You reported being in Stage 1 for 1 week, time to move to Stage 2!"
- 4. Participants will be recommended to move to Stage 3 of RTS after 14 days
 - o If the participant reports RTS Stage 2 for 14 days, they will receive the message "You reported being in Stage 2 for 2 weeks, time to move to Stage 3!"
- 5. Once in RTS Stage 3, participants cannot move back to Stage 2.
 - o If the participant reports RTS Stage 3 and moves back to RTS Stage 2, they will receive the message "Once your reach RTS Stage 3, you should not return to RTS Stage 2".

- 6. Participants are recommended to complete RTA and RTS Stage 1-3 together.
 - o If the participant reports RTA Stage 3 while in RTS Stage 1 or 2, they will receive the message "Remember, RTS and RTA Stage 1 to 3 should go together!"
- 7. Participants will be cautioned when they try and skip a stage
 - o If the participant skips from RTS Stage 2 to RTS Stage 4, they will receive the message "You forgot RTS Stage 3, we recommend you log this stage first!"
- 8. Participants will be cautioned when they try to move back a stage.
 - o If the participant moves back a Stage i.e., RTS Stage 5 to Stage 4, RTA 5 to Stage 4 they will receive the message "*Are you sure you want to move back a stage?*"
- 9. Participants cannot progress to a new stage of RTA/RTS if 2 or more symptoms worsen
 - o If the participant reports that 2 or more symptoms worsen (from morning to evening survey), **and** the participant attempts to progress to a new stage, they will receive the message "We recommend you do not progress to a new stage and inform a parent of your symptoms".

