Page 1: Current symptoms - App generates what was reported yesterday - Global "How are you" question Page 2: New Symptoms	"Please select what cognitive activities you have been doing today" 1. School work 2. Test/Quiz 3. Study 4. Socialize with friends 5. Text/phone friends 6. Use iPhone Apps i.e. Snapchat 7. Play on the iPad 8. Watch T.V. 9. Watch a YouTube video 10. Watch a movie 11. Play video games 12. Play a board game 13. Read/Re-read a book 14. Listen to music 15. Puzzles 16. Other	"Please rate 1-5 what you've been doing today" Cognitive Scale "What Stage of the RTS protocol are you in? Select: 1, 2, 3, 4, 5" "What Stage of the RTA protocol are you in? Select: 1, 2, 3, 4, 5" "What physical activities did you do today?" 1. Jog 2. Bike 3. Hike 4. Swim 5. Stretch/Yoga 6. Skate 7. Play Catch 8. Passing, shooting drills 9. Dribbling/Stickhandling 10. Throwing/Passing drills 11. Sports-specific drills 12. Basketball 13. Soccer 14. Football 15. Hockey 16. Rugby 17. Resistance training 18. Track and Field 19. Squash/Tennis 20. Other "Daily Symptom survey"

Daily Symptom survey

Page 1: Current symptoms

- App generates what was reported yesterday
- Global "How are you" question

Page 2: New Symptoms

"Please select what cognitive activities you have been doing today"

- 1. School work
- 2. Test/Quiz
- 3. Study
- 4. Socialize with friends
- 5. Text/phone friends
- 6. Use iPhone Apps i.e. Snapchat
- 7. Play on the iPad
- 8. Watch T.V.
- 9. Watch YouTube videos
- 10. Watch a movie
- 11. Play video games
- 12. Play a board game
- 13. Read/Re-read a book
- 14. Listen to music
- 15. Puzzles
- 16. Other

"Please rate 1-5 what you've been doing today"

Cognitive Scale

"What Stage of the RTS protocol are you in? Select: 1, 2, 3, 4, 5"

"What Stage of the RTA protocol are you in? Select: 1, 2, 3, 4, 5"

"What physical activities did you do today?"

- 1. Run
- 2. Jog
- 3. Bike
- 4. Hike
- 5. Swim
- 6. Stretch/Yoga
- 7. Skate
- 8. Play Catch
- 9. Jumping jacks/Burpees
- 10. Passing, shooting drills
- 11. Dribbling/Stickhandling
- 12. Throwing/Passing drills
- 13. Sports-specific drills
- 14. Basketball
- 15. Soccer
- 16. Football
- 17. Hockey
- 18. Rugby
- 19. Resistance training
- 20. Track and Field
- 21. Squash/Tennis
- 22. Other

"Daily Symptom survey"

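### App rule 2 does not fit its own trigger: as printed, the warning against entering RTA Stage 4 cannot clear, even for a youth who has completed full return to school

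*Combined protocol and SAP*

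**What the plan says.** The rules are in Appendix 1.1 (Business Rules for In-App Notifications).

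- **Rule 1, heading:** "Participants cannot enter RTA Stage 4 until they have completed RTS Stage 1-3". **Trigger:** "If the participant reports RTA Stage 4 when they are in RTS Stage 1 or 2 they will receive the message", followed by a reminder that Stages 1 to 3 come first.
- **Rule 2, heading:** "Participants must complete RTS Stage 5 (Full Return to School) before they can enter RTA Stage 4". **Trigger:** "If the participant reports RTA Stage 4 or 5 when they are in RTS Stage 3 through 5, they will receive the message". **Message:** "You should complete RTS Stage 4-5 before RTA Stage 4-6".

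The Background (section 2) fixes the number of school stages: "There are five stages in the CanChild RTS protocol". It gives six for RTA.

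The stage question in Appendix 1.2 (In-App Surveys) reads "What Stage of the RTS protocol are you in? Select: 1, 2, 3, 4, 5". The RTA question printed next to it also stops at 5. Neither offers an answer for having finished the last stage.

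Section 8 (Design) lists the time taken through the six RTA stages as a secondary outcome, and its Time to Stage paragraph says that stages are reported by the participants in both arms.

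**The concern.** A rule that warns until a condition is met needs a state in which the condition counts as met. Rule 2 has none: its heading asks for completion of RTS 5, its trigger includes RTS 5, and nothing can be reported after RTS 5. A youth whom the protocol would describe as fully back at school is still told to finish the school stages.

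This falls at the step back towards sport, and only in the App arm. The notifications are one component of the intervention, meant to support adherence to the guidelines. Stage is self-reported, so a warning that never clears could change what a youth logs, or when. That bears on time through the RTA stages. It also bears on the accuracy of the background algorithm, because section 9.5 compares the algorithm with self-reported stage.

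**Working it through.** The plan gives no figure to reproduce here. The check applies the printed triggers of rules 1 and 2 to each combination of reported stages.

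**Inputs**
- Reportable RTS stages: 1 to 5 (Appendix 1.2; five stages in section 2).
- Rule 1 fires if RTA = 4 and RTS is 1 or 2.
- Rule 2 fires if RTA is 4 or 5 and RTS is 3, 4 or 5.
- RTA 6 exists in the guideline but is not among the printed survey answers.

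**Result**

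| RTS reported | RTA 4 reported | RTA 5 reported | RTA 6 (not offered in the printed survey) |
|---|---|---|---|
| 1 | rule 1 | none | none |
| 2 | rule 1 | none | none |
| 3 | rule 2 | rule 2 | none |
| 4 | rule 2 | rule 2 | none |
| 5 | rule 2 | rule 2 | none |

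**Reading the table**
1. RTA 4: 2 stages (rule 1) + 3 stages (rule 2) = 5 of 5 reportable RTS stages draw a warning. There is no unwarned entry to RTA 4.
2. RTA 5: 3 of 5 RTS stages draw a warning. The two that do not are RTS 1 and 2, the earliest school stages.
3. At RTS 5 the rule 2 message fires for RTA 4 and for RTA 5. No later RTS answer exists, so no report of RTS stage can switch it off.

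**Headings side by side.** For a youth in RTS 4, with Stages 1 to 3 done, rule 1's heading is satisfied and rule 2's is not. The stated thresholds differ by two school stages (RTS 4 and 5). Anyone who has completed RTS 5 has also completed RTS 1 to 3, so meeting rule 2 always meets rule 1. The triggers do not overlap: in the table no cell holds both rules.

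**Message against survey.** Rule 2's message names RTA 4 to 6 and its trigger names RTA 4 and 5. Since the printed RTA question ends at 5, the trigger already covers every reportable stage that the message names. The mismatch therefore lies in the survey list, which has five options for a six-stage guideline. Section 7 describes the self-rating as running to 5 or 6, so the printed list may not be what the App shows.

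**Neighbouring rules.** Rule 18 can praise a youth at RTA 4 for meeting the activity target with no RTS condition, while rule 2 warns the same youth. A youth who responds to the warning by logging a lower RTA stage meets rule 8, which queries any move backwards.

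**The case against.** The strongest reply is that being in RTS 5 is not the same as having completed it. Rules 11 to 13 recommend a minimum time in each stage (24 hours, 48 hours or 1 week, by symptom stratum), so a warning to a youth who has only just reached RTS 5 agrees with rule 2's heading. That stands for the first part of the time at RTS 5. It does not rescue the trigger, because completion can never be reported and the same warning continues afterwards. Nor does rule 1 keep to that distinction: it requires Stages 1 to 3 to be completed, yet its trigger leaves out a youth who is still in Stage 3.

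A reader might infer that rules 1 and 2 contradict each other outright. They do not. They are nested and their triggers are disjoint, so no youth receives two conflicting messages from them. Rule 1's heading is a looser threshold made redundant by rule 2.

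A reader might also infer that the App blocks progression or raises the risk of reinjury. The documents support neither. The rules describe messages and no lock-out, a surplus warning leans towards caution, and no path from it to repeat injury is shown.

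Exposure may also be short. Section 2 advises against high-level activity while symptoms last, section 7 ends the surveys two days after symptoms resolve, and the App is deleted at the follow-up interview. Finally, these are two of 19 rules, in an App that also offers charts, resources, activity goals and cognitive games. All of this limits the consequence. It leaves the mismatch within rule 2 in place.

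**Conclusion.** The point holds for rule 2 as printed. Its heading and its trigger do not fit at RTS 5, and the warning cannot clear. In terms of the rules, the extent is exact: 5 of 5 reportable RTS stages draw a warning when RTA 4 is reported, while 2 of 5 draw none from rules 1 or 2 when RTA 5 is reported. The looser threshold in rule 1 and the five-option RTA question are secondary inconsistencies.

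In terms of the trial, the size is unknown. The documents do not say how many App users reach RTA 4 while still completing surveys, nor how they respond to the message. Time through the RTA stages could be affected in either direction. An effect on either primary outcome is not shown.

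The conclusion assumes that the App follows Appendix 1.1 literally and has no unprinted completion logic. If the deployed App differs, the fault is in the appendix and not in the guidance that youth receive.

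**What to change.** The investigators should reconcile the headings and triggers of rules 1 and 2 with the stage options in Appendix 1.2, so that:
- one entry condition for RTA 4 is stated;
- the App can record that the condition has been met;
- the warning stops once it has been met;
- the treatment of RTA 5 at RTS 1 and 2, and of RTA 6, is stated on purpose;
- the survey's RTA options agree with the six stages.

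They should also compare the deployed App with Appendix 1.1 and record the App version and the date of any correction, so that stage data gathered under different rules can be told apart. Which entry condition is right is their decision and is not proposed here.

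The cost is an edit to the rules and the survey list, matching text in the two appendices, and a short re-test.

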Rules, precedingly referred to as 'business rules', were developed for in App notifications that follow the guidance of the RTA/RTS protocols for progression through the stages (Appendix 1.1) Symptoms, self reported stages and activities are measured daily in the morning, afternoon and evening. A summary of these surveys is found in appendix 1.2. The home screen of the App (appendix 1.3) summarizes the next survey time, current stage of return to school and activity the youth is reporting that day and the activity minute goals (based on their stage of recovery) and how many activity minutes are completed. Icons at the bottom direct users to 1) a summary page that will show this information as well as a graph of their current symptoms, 2) a charts page which has several graphs of their progress (symptoms, stages, heart rate and activity minutes), 3) resources including the CanChild guidelines for concussion recovery, symptom strata (or the type of recovery pattern they may be following), the playsafe cards for individual sport specific strategies and a list of activity suggestions for each stage of recovery and 4) a contact us page which gives the Research Team [contact] and Principal investigator contact info as well as a form for troubleshooting help. When youth fill out the surveys, if 2 or more symptoms are worse, a pop up option of texting or emailing the participant's parent appears (appendix 1.3) Notifications are also sent to youth who exceed their activity goals and the Back2Play App will send a cautionary message "You are doing too much!" if their heart rate goes above 180. Encouraging notifications are also programmed with business rules if participants stay in the same stage for extended periods or if their symptoms get worst.

A complimentary App was developed by [name] of our investigator team. This Brain Games App was designed to screen some typical neurocognitive functions affected by concussion. There are 5 "games" that take about 10 minutes to complete. These include 1)

finger-tapping, 2) divided attention, 3) memory for designs, 4) tracing and 5) face match. An 'in App notification' is triggered by the youth recording a progression in their RTS stage. "Let's do a brain teaser! Sign into The Back2Play Brain Games App for your brain game then complete your symptom survey!" If the challenging tasks result in increased symptoms, The App notifies them "The brain game can be hard, stay at this stage if you need too!"

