- 10. Participants cannot progress to a new stage of RTA/RTS if their total number of symptoms increases by 2.
 - o If the participant reports an increase in symptoms by 2 (from morning to evening survey) **and** the participant attempts to progress to a new stage, they will receive the message "We recommend you do not progress to a new stage and inform a parent of your symptom".

CanChild RTA/RTS Symptom Strata

- 11. Participants will be classified to Strata A (Symptom Free within 48 hours after Injury) if their initial symptoms disappear within 24 hours or after 24-48 hours a participant reports ≤ 2 symptoms.
 - o If symptoms worsen, a participant can transition to Strata B.
 - o If the participant reports that their symptoms disappear within 24 hours, they will receive the message "Take at least 24 hours for each Stage as you complete the guidelines".
- 12. Participants will be classified to Strata B (Symptom Free/Symptoms decreases within 1-4 weeks post injury) if the report > 2 initial symptoms at 50 hours and continue at > 2 for 1 week (168 hours) up to 4 weeks. If the child's symptoms decrease, but are still >2, the child should remain in stratum B.
 - o Once a participant is in Strata B, they can never go to Strata A.
 - o If a participant is in Strata B and progressing through Stages within 2 days, but symptoms are getting worse, the child should take longer to progress through the stages.
 - o If > 2 Symptoms for a month, move the participant to Strata C

- o Recommendation: "Take at least 48 hours for each Stage as you complete the guidelines".
- 13. Participants will be classified to Strata C (Symptomatic for more than 4 weeks) if they report ≥ 2 initial symptoms for ≥ 4 weeks, or if the participant has been in Strata B for 1 month.
 - Once a participant is in Strata C, they can never go to Strata A or B.
 - o Recommendation: "Take at least 1 week for each Stage as you complete the guidelines".

Increasing or Worsening Symptoms

- 14. Participants will be reminded to share their symptoms with their parents if their number of symptoms increases by 2
 - o If the participant reports 2 or more symptoms new symptoms, they will receive the message "We recommend you inform a parent of your symptoms".
- 15. Participants will be reminded to share their symptoms with their parents if 2 or more symptoms worsen.
 - o If the participant reports 2 or more symptoms worsen, hey will receive the message "We recommend you inform a parent of your symptoms".

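### Time-in-stage prompts (Appendix 1.1, rules 3 and 4) can tell a youth to move on while symptoms meet the plan's own hold condition (rules 9 and 10)

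*Combined protocol and SAP*

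**What the plan says.** Appendix 1.1 lists the rules that generate the App's messages. Two of them push progression through the RTS stages on elapsed time:

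- Rule 3: "If the participant reports RTS Stage 1 for 7 days, they will receive the message" to go to Stage 2.
- Rule 4: "If the participant reports RTS Stage 2 for 14 days, they will receive the message" to go to Stage 3.

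Two others restrain progression on symptoms:

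- Rule 9: "Participants cannot progress to a new stage of RTA/RTS if 2 or more symptoms worsen".
- Rule 10: "Participants cannot progress to a new stage of RTA/RTS if their total number of symptoms increases by 2".

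Both compare the morning survey with the evening survey, and both name RTS as well as return to activity (RTA). Their headings read as a bar. In operation each is a recommendation, and it has a second trigger besides symptoms: "the participant attempts to progress to a new stage, they will receive the message" advising against the move.

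Section 2 (Back2Play App) describes the triggers in general terms: "Encouraging notifications are also programmed with business rules if participants stay in the same stage for extended periods or if their symptoms get worst". It does not say what is sent when both apply. The same section describes a pop-up that offers to contact a parent when two or more symptoms are worse. Section 9.2 (Risks) says that App use stops at once if symptoms worsen, and resumes only after at least 24 hours of rest and symptom resolution.

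**The concern.** The messages are the core of the intervention, and Section 2 says the rules follow the RTA/RTS guidance on moving through stages. A prompt to advance that ignores symptoms can reach a youth on a day when the plan's own criterion says not to advance. If the youth complies while still worsening, the App gives the opposite advice. The recipients are symptomatic 10- to 18-year-olds who are asked to trust this guidance.

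Rules 5 and 8 add some weight. Once in RTS Stage 3, a youth who reports Stage 2 again is told not to go back, and backward moves in general are queried. A badly timed rule 4 prompt therefore encourages a step that the App then discourages reversing.

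**Working it through.** The plan gives no figure to reproduce on this point. The check is to read the triggers literally and list the cases they allow.

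**Inputs (Appendix 1.1).**
- Prompt: RTS Stage 1 reported for 7 days (rule 3), or RTS Stage 2 for 14 days (rule 4). No symptom term.
- Hold condition: at least two symptoms worse, or the count up by two, morning to evening (rules 9 and 10).
- Hold message: hold condition **and** an attempt to progress.

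**Cases at each prompt point.**

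| Hold condition met | Attempt to progress | Move-on prompt | Hold message |
|---|---|---|---|
| no | no | sent | not sent |
| no | yes | sent | not sent |
| yes | no | sent | not sent |
| yes | yes | sent | sent |

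With two prompt points there are 2 × 2 × 2 = 8 combinations. The prompt is sent in 8 of 8. The hold condition is met in 4 of 8. Of those 4, the hold message is sent in 2 and not in the other 2.

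**Timing.** The last row need not be a same-day pair. Appendix 1.2 lists the stage question once a day (in the morning at the Stage 1 first assessment, in the evening from Stage Two), so an attempt and its hold message may come the day after the prompt. The documents do not give a sending time for the prompt, and the hold condition cannot be known before the evening survey.

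**Does any other provision cancel the prompt?**
- Rules 14 and 15 tell the youth to inform a parent; rule 15 reads "Participants will be reminded to share their symptoms with their parents if 2 or more symptoms worsen". Rule 16 says to slow down if symptoms are worse at all three surveys in a day. These add messages and withdraw none.
- The parent pop-up in Section 2 likewise adds a message only.
- Rule 12 does slow progression ("but symptoms are getting worse, the child should take longer to progress through the stages"), but only for Strata B youth who are moving through stages within 2 days. It does not cover someone who has sat in one stage for 7 or 14 days.
- No rule states an order of precedence.
- The Section 9.2 stop would prevent the prompt if it were applied. Appendix 1.1 does not code it, and rules 9, 10 and 14 to 16 all assume that a youth with worsening symptoms is still using the App.

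**The case against.** The strongest reply is Section 9.2: if App use really stops on worsening, the conflict never arises. That is right as far as it goes. But the stop appears only in the risk text, and the rule set is written for continued use. The two parts need reconciling whichever one governs.

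Second, the step itself is covered, because a youth who tries to progress while worsening does get the hold message. This stands, and it limits the gap to a prompt given before any attempt and to the reversal of advice that may follow.

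Third, time-based return to school may be deliberate. Rule 5 and the statement in Section 2 that rest is not isolation fit that reading, and the Section 2 bar on activity while symptomatic concerns physical activity, not school stages. The published guideline would be needed to settle this and is not available here. The point therefore does not claim that timed prompts are wrong. It says only that they are not reconciled with the hold condition written a few rules later.

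Fourth, the case counts largely restate that a symptom term is absent. That is fair. They show which combinations the rules allow and nothing about how often they occur.

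A reader might also infer that rule 18's praise for meeting the activity recommendation at RTA Stage 4, which has no symptom term either, is a second fault. The documents do not support that. Rule 18's heading treats the values as ceilings, so the praise may reward staying within a limit. The high-level activity barred in Section 2 is undefined, and rule 18's step bands place vigorous activity at Stages 5 and 6. Rules 11 to 13 foresee progression with some symptoms. It is at most a question for the clinical leads.

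**Conclusion.** The point holds for rules 3 and 4. As written, they can prompt a move between RTS stages while the rule 9 or 10 symptom condition is met, with no hold message unless the youth tries to move. The prompt is sent in all 4 of the 8 combinations where the condition is met, and 2 of those 4 carry no hold message.

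This rests on a literal reading of Appendix 1.1 and on the Section 9.2 stop not being enforced within the App. If that stop is enforced operationally, what remains is an inconsistency between two parts of the protocol.

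Two stronger conclusions might be inferred and should not be. The documents do not show that conflicting messages are common, because they give no data on how often worsening coincides with day 7 or day 14. Nor does this threaten the validity of the randomised comparison. It is a minor safety and consistency correction.

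**What to change.** Change the conditions on rules 3 and 4 only:

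1. Evaluate the prompt after the evening survey.
2. If the rule 9 or rule 10 symptom condition is met that day, whether or not the youth has tried to progress, hold the prompt. Send it on the first later day the condition is not met, if the youth is still in that stage.
3. If the morning or evening survey is missing, send the prompt as now, so that missed surveys cannot postpone it indefinitely.
4. Reconcile this with Section 9.2: state whether App use stops on worsening, and either build the stop into Appendix 1.1 or amend the risk text.

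The cost is two edited rules in an App that the Phase 2 description says is already being updated, plus re-testing and a protocol amendment. The symptom data are already collected; surveys, stage reporting, visits and outcome definitions do not change. The downside is that a prompt may be delayed by a day or more while worsening persists. Step 3 also leaves a small gap: on a day with a missing survey the prompt can still go to a youth who is worsening.
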